6.16 Pharmacokinetics

Pharmacokinetic blood samples will be collected for measurement of tideglusib and its primary metabolite, NP04113. PK samples will be collected at Visits and (corresponding to Weeks and and and will be collected at Visit and samples at Visit and the time of food and type of food before and after dosing is recorded for Visits where PK is collected.

Plasma concentrations of tideglusib and its primary metabolite NP04113 will be listed and summarised over time using the PK analysis set. The descriptive statistics will include the geometric mean and the number of subjects with a BLQ concentration. Concentrations reported as below the limit of quantification (BLQ) will be taken as zero for linear plots and descriptive statistics, and equal to the lower limit of quantification (LLOQ) for semi-logarithmic plots and the calculation of geometric means.

Individual plasma concentration profiles will be plotted both on the original scale and on the log scale separately. Mean (±SD) and median plasma concentration profiles will be plotted on the original scale and on the log scale.

A population pharmacokinetic analysis will be conducted. This is outside the scope of this SAP.

6.17 Safety Evaluation

The safety and tolerability of tideglusib will be assessed based on adverse events, and safety evaluations including clinical laboratory evaluations, vital signs and ECGs. This will be done for the SAF set. In addition, summarized for the RIS set.

6.17.1 Adverse Events

Adverse events (AEs) will be coded using the MedDRA dictionary version applicable at eCRF go-live. The version used will be indicated in the data summaries and listings.

A Treatment-Emergent AE (TEAE) is defined as an AE that started on or after the start of the first dose of double-blind, randomized study treatment. If adverse event dates are incomplete and it is not clear whether the adverse event was treatment-emergent, it will be assumed to be treatment-emergent.

A Non-Treatment Emergent Adverse Event (NTEAE) is defined as an AE that started before the administration of randomized study treatment.

A "double-blind treatment period" TEAE is defined as an AE that started on or after the start of randomized study treatment but before 2 days after randomized treatment was discontinued. A "post treatment period" TEAE is defined as an adverse event that started from 2 days after the randomized study treatment being discontinued.

A treatment related TEAE is defined as a TEAE that is related to the randomized study treatment. If the TEAE has a missing relationship it is assumed to be related to the randomized study treatment for analysis purposes.

The following summaries of the total number of "double-blind treatment period" TEAEs, "post treatment period" TEAEs and all TEAEs (both "double-blind treatment period" and "post treatment period" TEAEs) will be provided at the event and subject levels as indicated:

- TEAEs (number of events and number of subjects).
- Serious TEAEs (number of events and number of subjects).
- Serious randomized study treatment-related TEAEs (number of events and number of subjects).
- TEAEs by severity (mild/moderate/severe) (number of events and number of subjects).
- TEAEs by relationship to randomized study treatment category (unrelated/related) (number of events and number of subjects).
- TEAEs leading to discontinuation from the study (number of subjects only).
- Randomized study treatment-related TEAEs leading to discontinuation from the study (number of subjects only).
- TEAEs leading to death (number of subjects only).

The following summaries of NTEAEs will be provided at the event and subject levels as indicated:

- NTEAEs (events and subjects).
- NTEAEs by severity (mild/moderate/severe) (events and subjects).
- Serious NTEAEs (events and subjects).
- NTEAEs leading to withdrawal (subjects only).
- NTEAEs leading to death (subjects only).

In the above summaries, if a subject experienced more than one NTEAE/TEAE, the subject will be counted once using the most related event for the "by relationship to treatment" summary and the worst severity for the "by severity" summary. The Enrolled analysis set will be used to summarize NTEAEs.

A table of TEAEs by System Organ Class (SOC) and Preferred Term (PT) will be presented for the following:

- Events and subjects for "double-blind treatment period" TEAEs, "post treatment period" and all TEAEs.
- Events and subjects for "double-blind treatment period" treatment-related TEAEs, "post treatment period" and all treatment-related TEAEs.
- Events and subjects for "double-blind treatment period" serious TEAEs, "post treatment period" and all serious TEAEs.
- Events and subjects for all NTEAEs.

For all of the above, SOC and PT will be presented in decreasing frequency of the total number of subjects with TEAEs. If a subject experienced more than one TEAE, the subject will be counted once for each SOC and once for each PT.

A table of TEAEs by severity, System Organ Class (SOC) and Preferred Term (PT) will also be presented. If a subject experienced more than one TEAE, the subject will be counted once for each SOC and once for each PT at the most severe event.

Adverse event data will be listed in full and this will also include a treatment emergent flag, a double-blind treatment period TEAE flag, a post treatment period TEAE flag, the time of onset and cessation of event relative to first dosing of randomized study treatment and duration of AE.

TEAEs leading to death or AEs leading to death which will also include a treatment emergent flag, serious TEAEs and TEAEs leading to discontinuation of study drug will also be listed.

6.17.2 Clinical Laboratory Evaluation

Observed values and change from baseline in and assessments will be summarized over time. At baseline the change from run-in baseline will also be presented. If the test results are reported in categorical format, the results will be summarized by subject counts and percentage for each category.

Each parameter will be classed as low, normal, high based on the reference ranges. Shift tables in relation to the normal range from baseline over time will be presented.

virology and urinalysis data will be listed separately including change from baseline, reference ranges flagging all out of range values and their clinical significance. Separate listings of out of range laboratory measurements recorded throughout the study will be provided. Local laboratory results will be presented on the same listings, where these are collected.

Spaghetti plots of and will be produced containing a separate line for each subject, with the measured value appearing on the y-axis and time (days since first administration of randomized study treatment) on the x-axis. The relevant reference range and 1 x, 2x and 3x Upper Limit of Normal (ULN) will be overlaid on the plot as a reference line.

6.17.3 Vital Signs

Observed values and changes from baseline for weight, pulse rate, respiration rate, systolic blood pressure, diastolic blood pressure and body temperature will be summarized over time. At baseline the change from run-in baseline will also be presented.

Parameters will be presented in the same order as the eCRF.

All vital sign data will be listed including reference ranges flagging all out of range values and changes from baseline/run-in baseline. Changes from baseline in vital signs of clinical concern recorded throughout the study will also be flagged. Changes of clinical concern are defined as a change from baseline in systolic blood pressure of more than 40 mmHg, a change from baseline in diastolic blood pressure of more than 20 mmHg, or a change from baseline in heart rate of more than 30 bpm.

A listing of subjects with at least one vital sign of clinical concern recorded throughout the study will be provided.

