6.2 Secondary Objectives

Secondary Objectives of this study are:

- To evaluate the safety and tolerability of weight adjusted 1000 mg tideglusib compared to placebo in children and adolescents with Congenital DM1
- To evaluate the efficacy, from baseline to end of treatment, of weight adjusted 1000 mg tideglusib compared to placebo in children and adolescents with Congenital DM1 as measured by clinician-completed, caregiver-completed rating scales, functional assessments, and biomarker/physiological assessments
- To evaluate the blood pharmacokinetics of tideglusib and its main metabolite (NP04113) after repeat dosing in children and adolescents with Congenital DM1
- To evaluate the consistency of telehealth data and in-clinic data for the CDM1-RS and CGI rating scales

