8. STUDY DESIGN

8.1 Study Endpoints to be assessed:

Primary Efficacy Endpoint:

• Clinician-Completed Congenital DM1 Rating Scale (CDM1-RS)

Key Secondary Efficacy Endpoint:

• Clinical Global Impression - Improvement Scale (CGI-I)*

-

^{*} Sometimes referred to as the CGI-C

Protocol No: AMO-02-MD-2-003 AMO Pharma Ltd.

Secondary Efficacy Endpoints:

- Top 3 Caregiver Concerns VAS score
- Caregiver Completed Congenital DM1 Rating Scale (CC-CDM1-RS)
- Clinical Global Impression Severity Scale (CGI-S)
- CDM1-RS Independent Central Rater Score
- CGI-I Independent Central Rater Score
- CGI-S Independent Central Rater Score
- 10 Meter Walk/Run (preferred speed and fastest speed)

Exploratory Endpoints:

- DXA Scan measurement of total body lean/muscle mass
- Measurement of lip strength (via lip force meter)
- Congenital and Childhood Myotonic Dystrophy Health Index (CC-MDHI) Parent Proxy Instrument
- Autism Behavior Inventory- Clinician (ABI-C)
- and Adaptive Behavior Composite standard scores of the Vineland Adaptive Behavior Scale -
- Quantitative myometric measure of hand grip strength
- NIH Toolbox Cognition Battery: Dimensional Change Card Sort Test
- NIH Toolbox Cognition Battery: Picture Sequence Memory Test
- Peabody Picture Vocabulary Test (PPVT)
- levels
- sample
- •
- Serial blood pharmacokinetics of tideglusib

Safety Endpoints:

• The incidence of Adverse events (AEs), including serious adverse events (SAEs), between Screening and end of treatment. The incidence will also be assessed during a follow-up period after discontinuation of the study drug for those subjects not participating in the extension study AMO-02-MD-2-004.

Investigational Medicinal Product: Tideglusib

Protocol No: AMO-02-MD-2-003 AMO Pharma Ltd.

• The incidence of abnormal findings in objective assessments (e.g. laboratory values, ECGs, vital signs and bone mineral density) between Screening and end of treatment. The incidence of abnormal findings in objective assessments will also be assessed during a follow-up period after discontinuation of the study drug for those subjects not participating in the extension study AMO-02-MD-2-004.

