- The incidence of Adverse events (AEs), including serious adverse events (SAEs), between Screening and end of treatment. The incidence will also be assessed during a follow-up period after discontinuation of the study drug for those subjects not participating in the extension study AMO-02-MD-2-004.
- The incidence of abnormal findings in objective assessments (e.g. laboratory values, ECGs, vital signs and bone mineral density) between screening and end of treatment. The incidence of abnormal findings in objective assessments will also be assessed during a follow-up period after discontinuation of the study drug for those subjects not participating in the extension study AMO-02-MD-2-004.

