6 ANALYSIS PLAN

6.1 General

Summary statistics for continuous variables will consist of number of non-missing observations (n), mean, standard deviation (SD), minimum, median, maximum, 25th and 75th percentiles unless specified otherwise.

For categorical variables the number and percentage of subjects in each category will be presented, based on the number of subjects in the analysis set, unless otherwise specified.

All statistical tests will be performed using a two-tailed 5% overall significance level, unless otherwise stated. The null hypothesis at all times will be that the treatments are equivalent. All comparisons between the treatments will be reported with 95% confidence intervals for the difference.

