6.5 Data presentations

The TFLs will present treatment group (i.e. tideglusib or placebo).

TFLs on the PKAS, SAF and FAS analysis sets will be presented according to the treatment actually received (i.e. tideglusib or placebo), regardless of the randomization.

TFLs on the Enrolled, ITT and PPS analysis sets will be presented according to the randomized treatment group.

The data will be summarised in tabular form by treatment group apart from disposition of subjects, protocol deviations and background and demographic data which will be summarised by treatment group and overall subjects.

Only scheduled post-baseline laboratory, vital signs and ECG values will be tabulated, post-baseline repeat/unscheduled assessments will be listed only; all clinically significant values will be noted.

Individual subject assignments to each analysis set will be summarized using the Enrolled set. The primary and key secondary efficacy endpoints will be summarised using the ITT and the PPS. All other secondary endpoints will be summarised using the ITT. PK concentration data will be summarised using the PKAS set and all other data will be summarized using the SAF set. Additionally, run-in data for efficacy and adverse events will be summarised for the RIS set.

Eligibility, completion/withdrawal, consent/assent, analysis set, protocol deviations, demographic and other background listings in section 6.8 and visit dates will be based on the enrolled set, PK listings will be based on the PKAS set, efficacy listings, run-in treatment, study drug dispensing and return, study drug daily dosing and meal intake data, all adverse events and adverse events leading to death will be based on the RIS set and all other listings will be based on the SAF set. Listings based on

the RIS will presented according to the randomized treatment for the efficacy listings and actual treatment received otherwise.

Graphical presentations of the data will also be provided where appropriate. Unless otherwise stated, only data from Visit onwards will be presented graphically.

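### Vital signs belong to an incidence endpoint, but SAP 6.17.3 uses its own concern criteria only for flags and a listing, with no number and percentage by arm

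*SAP*

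**What the plan says.** The second safety endpoint in Protocol 8.1 is "The incidence of abnormal findings in objective assessments (e.g. laboratory values, ECGs, vital signs and bone mineral density) between Screening and end of treatment". SAP 2.3 repeats it. Both documents extend it to the follow-up period for children who do not enter the extension study. The related secondary objective in Protocol 6.2 is "To evaluate the safety and tolerability of weight adjusted 1000 mg tideglusib compared to placebo in children and adolescents with Congenital DM1".

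For vital signs, SAP 6.17.3 plans the following:

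- Summaries of observed values and changes from baseline for weight, pulse rate, respiration rate and others: "systolic blood pressure, diastolic blood pressure and body temperature will be summarized over time". SAP 6.1 fixes what such a summary contains: the number of observations, then "mean, standard deviation (SD), minimum, median, maximum, 25th and 75th percentiles unless specified otherwise".
- Numeric criteria: "Changes of clinical concern are defined as a change from baseline in systolic blood pressure of more than 40 mmHg", with matching limits of 20 mmHg for diastolic pressure and 30 bpm for heart rate.
- Two uses of those criteria: a flag in the full data listing, and a separate listing of the children who meet one ("A listing of subjects with at least one vital sign of clinical concern recorded throughout the study will be provided").

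SAP 6.5 confines laboratory, vital sign and ECG tables to scheduled values; for the rest, "post-baseline repeat/unscheduled assessments will be listed only; all clinically significant values will be noted".

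**The concern.** An incidence in a placebo-controlled trial needs a numerator and a denominator in each arm. For vital signs, the SAP goes as far as choosing thresholds and then stops before the table that would give the numerator. Continuous by-visit statistics describe the centre and spread of the measurements. They do not say how many children crossed a limit at least once.

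What is at stake is the completeness of safety reporting in a paediatric trial. For one named component of a declared endpoint, the clinical study report would carry an arm-level figure only where an investigator had recorded an adverse event. A reader who wanted the count by the SAP's own criteria would have to assemble it from a listing.

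**Working it through.** No power, error-rate or effect figure is involved. The check is whether any planned output gives a number and percentage by arm for the three criteria.

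**Step 1. Where the criteria are used.** In SAP 6.17.3 each of the three (systolic, diastolic, heart rate) feeds a listing flag and the listing of affected children. None feeds a table. Criteria tabulated by arm: 0 of 3.

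**Step 2. Components named in the same endpoint sentence.**

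- ECG (SAP 6.17.4, Table 3): number and percentage of subjects in 5 categories of absolute interval and 3 categories of increase, 5 + 3 = 8 categories.
- Laboratory (SAP 6.17.2): low, normal or high classes, with shift tables from baseline.
- Vital signs (SAP 6.17.3): neither form.

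The ECG and laboratory tables are by visit and use scheduled values only, so they are not ever-during-treatment counts either. The contrast is that they have a categorical table by arm and vital signs have none.

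**Step 3. Other routes to a count.**

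- *Adverse event tables (SAP 6.17.1).* Protocol 10.2.6 has an abnormal vital sign recorded as an adverse event when the investigator considers it clinically significant. Those events are then counted by treatment. A child who crosses a SAP threshold without that judgement is not counted.
- *Post hoc safety summaries (SAP 6.12).* Worst-case post-baseline summaries are mentioned, but they are optional and depend on what the COVID-19 missing-data summaries show.
- *SAP addendum (August 2024).* It contains no vital sign output.
- *Table shells.* SAP 1 places them in a separate document, which was not available.

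**Step 4. Scale of the missing table.** SAP 3 gives 53 children randomised 1:1, and 53 / 2 = 26.5, so about 26 or 27 per arm (assuming nearly all were dosed and so are in the safety set). One child is 1/27 = 3.7%. If no child in an arm of 26 met a criterion, the exact 95% upper limit would be 1 − 0.025^(1/26) = 13.2%. The table can therefore describe, but it cannot support a formal comparison.

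**The case against.** The case on the other side has real force.

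- *The promised analysis is delivered.* The protocol synopsis, under statistical methods for safety, promises only that vital signs and their changes from baseline will be summarised, and SAP 6.17.3 does that. This stands as far as it goes. The synopsis section on safety assessments, however, also says the incidence of abnormal objective findings will be assessed, and the endpoint wording is the same in both documents.
- *The concern criteria are not the endpoint.* No text equates abnormal findings with the three thresholds, and the protocol's own test of an abnormality that matters is investigator judgement, which reaches the adverse event tables. This also stands. It means one route to incidence by arm exists, and a reader who infers that the endpoint goes wholly unreported for vital signs would be wrong. It does not cover threshold crossings that the investigator did not consider significant.
- *The information is already in the listing.* Under SAP 6.5 the vital sign listings are on the safety set, with treatment received. With 53 children a short listing gives the numerator, and the arm totals give the denominator. This stands and sets the weight of the point. It is tempting to argue that the summary statistics leave the number of affected children uncertain. The documents do not support that reading, because the count would come from the listing, which identifies each child.
- *A fix should not go beyond its comparators.* The ECG and laboratory tables use scheduled values. A count that included unscheduled visits would give children seen more often more chances to appear. This is accepted and shapes the fix.

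**Conclusion.** The gap is real but minor. In the SAP text, 0 of 3 vital sign criteria are given a number and percentage by arm, against 8 of 8 ECG categories. Apart from investigator-judged adverse events, the vital sign part of the endpoint is left to listings. No child is hidden and no data are lost. Nothing here bears on the efficacy analysis or on the care of the children.

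The conclusion rests on two conditions. First, the table shells were not seen; if one already holds this table, the SAP text only needs to call for it. Second, the three concern criteria are taken as a reasonable working definition of an abnormal vital sign because the SAP itself chose them, not because either document says they define the endpoint.

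**What to change.** In SAP 6.17.3, add one descriptive table on the safety set, by treatment received:

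- Number and percentage of children with at least one post-baseline change of clinical concern, for each of the three existing criteria and for any of them. Heart rate is taken as the pulse rate recorded with the vital signs.
- Changes in either direction counted, since the criteria state none.
- The treatment period and follow-up shown separately, as the endpoint does.
- Main row on scheduled values, consistent with SAP 6.5. A second row includes unscheduled values, with a footnote that children with more unscheduled visits have more chances to be counted.
- No hypothesis test.

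If the analyses have already been run, the table can be issued as a labelled additional output, as the August 2024 addendum did for its own additions.

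The cost is a few lines of SAP text and one table built from flags already planned for the listing. The drawback is sparse rows that must be read descriptively. Trial conduct and data collection do not change.

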6.17.4 Electrocardiography

All ECGs will be performed using equipment provided by the central ECG provider and all ECGs performed will be transmitted electronically to the central ECG provider for interpretation. For any visits completed in a subject's home due to a COVID-19 related reason, the standard 12-lead ECG will be replaced with a 6-lead ECG using equipment provided by the central ECG vendor. The investigator will perform the initial interpretation of the ECG immediately after collection to ensure the safety of each subject. The central ECG provider will also provide an interpretation.

ECG parameters will include heart rate, PR interval, QRS interval, QT interval, and QTcF and QTcB intervals (QT interval corrections will be those values provided by the central ECG provider).

ECG observed values and changes from baseline/run-in baseline will be summarized over time by timepoint (if applicable), Type (12-lead or 6-lead) for each parameter.

For overall interpretations if more than one value is recorded per assessment, then the most severe of the respective readings will be taken.

The number and percentage of subjects meeting the following categories will be tabulated over time by timepoint (if applicable):

Table 3: AMO-02-MD-2-003 ECG Criteria

| Parameter | Criteria |
|--|---|
| QT and QTcF/QTcB intervals | <450 msec ≥ 450 msec and < 480 msec * ≥ 480 msec and < 500 msec * ≥ 480 msec * ≥ 500 msec * |
| Increase from Baseline/Run-in baseline in QT and QTcF/QTcB intervals | < 30 msec ≥ 30 msec and < 60 msec * ≥ 60 msec * |

^{*} values of potential clinical importance

In addition, the overall interpretation according to the investigator of the ECG (Normal, Abnormal Not Clinically Significant, and Abnormal Clinically Significant) will be summarized over time.

Shift in ECG overall interpretation according to the investigator over time for normal, abnormal not clinically significant, abnormal clinically significant and missing results will be summarised.

Similar summaries for the central ECG provider interpretation will also be made.

Parameters will be presented in the same order as the CRF.

All ECG results will be listed including changes from baseline/run-in baseline values. QT, QTcF and QTcB values of \geq 480 msec and \geq 500 msec and increases from baseline \geq 60 msec will be flagged.

